15.3 Timepoint Labelling

Table 16: Timepoint Labels

Analysis Visit	Timepoint	Output Label
Day 1	15 minutes pre-COMP360	pre-dose
	1 hour post-COMP360	1 hour
	3 hours post-COMP360	3 hours
	6 hours post-COMP360	6 hours

15.4 Baseline Definitions

Table 17: Baseline Definitions

Parameter	Baseline
Safety	
All	Day -1
Vital Signs	Day 1 (pre-COMP360 administration)
Efficacy	
All	Day -1

15.5 Study Day and Duration Derivation

Study day, defined as the number of days from the dose of COMP360, will be derived as follows:

- date of event – date of dose of COMP360 + 1, for events on or after dose
- date of event – date of dose of COMP360, for events before dose

Duration of AEs (in days) will be calculated as follows:

- [stop date of the event – start date of the event + 1] or
- [(stop datetime of the AE-start datetime of the AE)/(60×60×24)]

In cases where the time component of either the start or the stop date is missing the following approach will be taken:

- If the AE start time is missing and the AE occurred after Day 1, the duration will be calculated assuming the event started at 00:00:00 AM of that day, otherwise if the AE occurred on Day 1 the duration will be derived using the datetime of dosing as starting point.
- If the AE stop time is missing the duration will be calculated assuming the event stopped at 23:59:59 (11:59:59 PM) of that day.

15.6 Decimal Places

Decimal places (dps) for derived data described in Section 8 will be determined by the scale of measurement unless otherwise stated. No dps will be displayed if the smallest calculated value is ≥ 100 ; 1 dp will be displayed when the smallest value is within the interval (10, 100), with 10 being inclusive; 2 dps will be displayed when the smallest value is within (1, 10), with 1 being inclusive; and so on for even smaller scales of measurement.

Derived data where it is known in advance the result will be an integer for example day, month, year, number of days and total scores (for rating scales) will be presented with zero dps.

Means, medians, and percentiles will be displayed to one more dp than the data, dispersion statistics (eg SD) will have two more dps, and the minimum and maximum will be displayed to the same number of dps as reported in the raw data. Percentages will be displayed with one dp. No percentage will be displayed for zero-frequency scenarios.

16 TABLES, FIGURES AND LISTINGS

The following tables include details of the tables, figures and listings to be created.

The following validation methods may be used:

- Independent programming of numbers and manual review of format (Iprog)
- Independent programming by statistician of numbers and manual review of format (Stat Iprog)
- Manual review (MR)
- Code review (CR)

Table 18: List of Tables, Figures and Listings

Table Number	Table Title	Validation Method	Shell Number (if Repeat)
14.1	Demographic Data		
14.1.1	Disposition		
14.1.1.1	Participant Disposition by Country – Screening Analysis Set	IProg	
14.1.1.2	Participant Disposition, Completions, and Early Terminations with Reasons – Safety Analysis Set	IProg	
14.1.1.3	Screen Failures with Reasons – Screening Analysis Set	IProg	
14.1.1.4	Important Protocol Deviations – Safety Analysis Set	IProg	
14.1.2	Demographics		
14.1.2	Demographics – Safety Analysis Set	IProg	
14.1.3	Baseline Characteristics		
14.1.3.1	Medical History – Safety Analysis Set	IProg	
14.1.3.2	Prior Medications – Safety Analysis Set	IProg	
14.1.3.3	Concomitant Medications – Safety Analysis Set	IProg	14.1.3.2
14.1.3.4	Prior Non-Drug Therapies – Safety Analysis Set	IProg	14.1.3.1
14.1.3.5	Concomitant Non-Drug Therapies – Safety Analysis Set	IProg	14.1.3.1
14.1.3.6	Prior Non-Drug Therapies for PTSD – Safety Analysis Set	IProg	14.1.3.1
14.1.3.7	Concomitant Non-Drug Therapies for PTSD – Safety Analysis Set	IProg	14.1.3.1
14.1.3.8	Other Baseline Characteristics – Safety Analysis Set	IProg	
14.1.3.9	Mini International Neuropsychiatric Interview (MINI, Version 7.0.2) – Safety Analysis Set	IProg	
14.1.3.10	Life Event Checklist for DSM-5 (LEC-5) – Safety Analysis Set	IProg	
14.2	Efficacy Data		
14.2.2	Secondary Efficacy Endpoints		
14.2.2.1	Secondary Endpoint – Summary of Clinician-Administered PTSD Scale for DSM-5 (CAPS-5) and Change from Baseline – Full Analysis Set	IProg	

Table Number	Table Title	Validation Method	Shell Number (if Repeat)
14.2.2.2	Secondary Endpoint – Summary of PTSD Checklist for DSM-5 (PCL-5) and Change from Baseline – Full Analysis Set	IProg	14.2.2.1
14.2.2.3	Secondary Endpoint – Summary of Sheehan Disability Scale (SDS) Total Score and Change from Baseline – Full Analysis Set	IProg	14.2.2.1
14.2.2.4	Secondary Endpoint – Summary of EQ-5D-5L Index Score and Change from Baseline – Full Analysis Set	IProg	14.2.2.1
14.2.2.5	Secondary Endpoint – Proportion of Clinician-Administered PTSD Scale for DSM-5 (CAPS-5) Responders Over Time – Full Analysis Set	Stat IProg	
14.2.2.6	Secondary Endpoint – Proportion of Clinician-Administered PTSD Scale for DSM-5 (CAPS-5) Remitters Over Time – Full Analysis Set	Stat IProg	14.2.2.6
14.2.3	Additional Efficacy Endpoints		
14.2.3.1	Additional Endpoint – Summary of Perceived Ability to Cope with Trauma (PACT) Scale Scores and Change from Baseline – Full Analysis Set	IProg	14.2.2.1
14.2.3.2	Additional Endpoint – Summary of Five-Dimensional Altered State of Consciousness (5D-ASC) – Full Analysis Set	IProg	
14.2.3.3	Additional Endpoint – Summary of Emotional Breakthrough Inventory (EBI) – Full Analysis Set	IProg	
14.3	Safety Data		
14.3.1	Displays of Adverse Events		
14.3.1.1	Summary of Treatment-Emergent Adverse Events (TEAEs) – Safety Analysis Set	IProg	
14.3.1.2	MedDRA Summary of Treatment-Emergent Adverse Events (TEAEs) by Primary System Organ Class and Preferred Term – Safety Analysis Set	IProg	
14.3.1.3	MedDRA Summary of Non-Serious Treatment-Emergent Adverse Events (TEAEs) with $\geq 5\%$ Incidence by Primary System Organ Class and Preferred Term – Safety Analysis Set	IProg	14.3.1.2
14.3.1.4	MedDRA Summary of Treatment-Emergent Adverse Events (TEAEs) by Primary System Organ Class, Preferred Term and Worst Severity – Safety Analysis Set	IProg	14.3.1.2
14.3.1.5	MedDRA Summary of Treatment-Emergent Adverse Events (TEAEs) by Primary System Organ Class, Preferred Term and Strongest Relationship to Study Drug – Safety Analysis Set	IProg	

Table Number	Table Title	Validation Method	Shell Number (if Repeat)
14.3.1.6	MedDRA Summary of Treatment-Emergent Adverse Events (TEAEs) by Primary System Organ Class, Preferred Term, Time of Onset and Duration of Adverse Event – Safety Analysis Set	IProg	
14.3.1.7	MedDRA Summary of Treatment-Emergent Serious Adverse Events (TESAEs) by Primary System Organ Class and Preferred Term – Safety Analysis Set	IProg	14.3.1.2
14.3.1.8	MedDRA Summary of Treatment-Emergent Serious Adverse Events (TESAEs) by Primary System Organ Class, Preferred Term, Time of Onset and Duration of Adverse Event – Safety Analysis Set	IProg	14.3.1.6
14.3.1.9	MedDRA Summary of Treatment-Emergent Adverse Events of Special Interest (AESIs) by AESI Term and Preferred Term – Safety Analysis Set	IProg	14.3.1.2
14.3.1.10	MedDRA Summary of Treatment-Emergent Adverse Events of Special Interest (AESIs) by AESI Term, Preferred Term, Time of Onset and Duration of Adverse Event – Safety Analysis Set	IProg	14.3.1.6
14.3.1.11	MedDRA Summary of Treatment-Emergent Adverse Events (TEAEs) Leading to Study Withdrawal by Primary System Organ Class and Preferred Term – Safety Analysis Set	IProg	14.3.1.2
14.3.1.12	MedDRA Summary of Treatment-Emergent Adverse Events (TEAEs) Occurring Within 24 Hours of Study Drug Administration by Primary System Organ Class, Preferred Term, and Start/Stop Time Since Study Drug Administration – Safety Analysis Set	IProg	
14.3.1.13	MedDRA Summary of Treatment-Emergent Adverse Events of Special Interest (AESIs) Occurring Within 24 Hours of Study Drug Administration by AESI Term, Preferred Term, and Start/Stop Time Since Study Drug Administration – Safety Analysis Set	IProg	14.3.1.12
14.3.1.14	MedDRA Summary of Pre-Treatment Adverse Events (Aes) by Primary System Organ Class, and Preferred Term – Screening Analysis Set	IProg	14.3.1.2
14.3.4	Laboratory Values		
14.3.4.1	Summary Statistics of Observed Values and Change from Baseline in Haematology – Safety Analysis Set	IProg	
14.3.4.2	Summary Statistics of Observed Values and Change from Baseline in Chemistry – Safety Analysis Set	IProg	14.3.4.1
14.3.4.3	Normal Range Shifts from Baseline in Haematology Values – Safety Analysis Set	IProg	
14.3.4.4	Normal Range Shifts from Baseline in Chemistry Values – Safety Analysis Set	IProg	14.3.4.3

Table Number	Table Title	Validation Method	Shell Number (if Repeat)
14.3.5	Vital Signs	IProg	
14.3.5.1	Summary Statistics of Observed Values and Change from Baseline in Vital Signs by Visit and Timepoint – Safety Analysis Set	IProg	
14.3.5.2	Overall Summary of Clinically Important Vital Signs Values – Safety Analysis Set	IProg	
14.3.6	Other Safety		
14.3.6.1	Summary Statistics of Observed Values and Changes from Baseline to Day 2 in ECG Variables – Safety Analysis Set	IProg	14.3.4.1
14.3.6.2	ECG Clinical Interpretation – Shift from Baseline to Day 2 – Safety Analysis Set	IProg	
14.3.6.3	Summary of QTc Interval Categories – Safety Analysis Set	IProg	
14.3.6.4	Summary of C-SSRS by Visit – Safety Analysis Set	IProg	
14.3.6.5	Summary of BPRS+ Total Score by Visit – Safety Analysis Set	IProg	
14.3.6.6	Summary of BPRS+ Symptom Score by Visit – Safety Analysis Set	IProg	

Figure Number	Figure Title	Validation Method	Shell Number (if Repeat)
14.2	Efficacy Endpoints		
14.2.2	Secondary Endpoints		
14.2.2.1	Secondary Endpoint – Summary of Clinician-Administered PTSD Scale for DSM-5 (CAPS-5) and Change from Baseline – Full Analysis Set	IProg	
14.2.2.2	Secondary Endpoint – Summary of PTSD Checklist for DSM-5 (PCL-5) and Change from Baseline – Full Analysis Set	IProg	14.2.2.2

Figure Number	Figure Title	Validation Method	Shell Number (if Repeat)
14.2.2.3	Secondary Endpoint – Summary of Sheehan Disability Scale (SDS) Total Score and Change from Baseline – Full Analysis Set	IProg	14.2.2.2
14.2.2.4	Secondary Endpoint – Summary of EQ-5D-5L Index Score and Change from Baseline – Full Analysis Set	IProg	14.2.2.2
14.2.2.5	Secondary Endpoint – Proportion of Clinician-Administered PTSD Scale for DSM-5 (CAPS-5) Responders – Full Analysis Set	Stat IProg	14.2.2.2
14.2.2.6	Secondary Endpoint – Proportion of Clinician-Administered PTSD Scale for DSM-5 (CAPS-5) Remitters – Full Analysis Set	Stat IProg	14.2.2.2
14.2.3	Additional Endpoints		14.2.2.2
14.2.3.1	Additional Endpoint – Summary of Perceived Ability to Cope with Trauma (PACT) Scales Scores and Change from Baseline – Full Analysis Set	IProg	14.2.2.2
14.3.5	Safety Endpoints		
14.3.5.1	Summary of Administration Day Vital Signs – Safety Analysis Set	IProg	
14.3.5.2	Individual Participant Plots of Administration Day Vital Signs – Safety Analysis Set	IProg	

Listing Number	Listing Title	Validation Method	Shell Number (if Repeat)
16.2	Participant Data Listings		
16.2.1	Discontinued Participants		
16.2.1.1	Details of Study Discontinuations – Safety Analysis Set	IProg	
16.2.1.2	Details of Study Completers – Safety Analysis Set	IProg	
16.2.2	Protocol Deviations		
16.2.2.1	Important Protocol Deviations – Safety Analysis Set	IProg	
16.2.3	Participation in each Defined Analysis Set		

Listing Number	Listing Title	Validation Method	Shell Number (if Repeat)
16.2.3	Analysis Sets – Screening Analysis Set	IProg	
16.2.4	Demographic Data		
16.2.4.1	Demographics – Safety Analysis Set	IProg	
16.2.4.2	Other Baseline Characteristics – Safety Analysis Set	IProg	
16.2.4.3	Medical History – Safety Analysis Set	IProg	
16.2.4.4	Inclusion Criteria – Screening Analysis Set	IProg	
16.2.4.5	Exclusion Criteria – Screening Analysis Set	IProg	
16.2.4.6	Prior Medications – Safety Analysis Set	IProg	
16.2.4.7	Concomitant Medications – Safety Analysis Set	IProg	
16.2.4.8	Prior Non-Drug therapies – Safety Analysis Set	IProg	
16.2.4.9	Concomitant Non-Drug Therapies – Safety Analysis Set	IProg	
16.2.4.10	Prior Non-Drug Therapies for PTSD – Safety Analysis Set	IProg	
16.2.4.11	Concomitant Non-Drug Therapies for PTSD – Safety Analysis Set	IProg	
16.2.5	Compliance And/Or Drug Concentration Data		
16.2.5	Study Drug Administration – Safety Analysis Set	IProg	
16.2.6	Individual Efficacy Response Data		
16.2.6.1	Clinician-Administered PTSD Scale for DSM-5 (CAPS-5) – Full Analysis Set	IProg	
16.2.6.2	PTSD Checklist for DSM-5 (PCL-5) – Full Analysis Set	IProg	
16.2.6.3	Sheehan Disability Scale (SDS) – Full Analysis Set	IProg	
16.2.6.4	EQ-5D-5L – Full Analysis Set	IProg	
14.2.6.5	Perceived Ability to Cope with Trauma (PACT) Scale – Full Analysis Set	IProg	
14.2.6.6	Resilience Adult Scale (RAS) – Full Analysis Set	IProg	
16.2.6.7	Five-Dimensional Altered State of Consciousness (5D-ASC) – Full Analysis Set	IProg	
16.2.6.8	Emotional Breakthrough Inventory (EBI) – Full Analysis Set	IProg	
16.2.7	Adverse Event Listings		
16.2.7.1	Treatment-Emergent Adverse Events (TEAEs) – Safety Analysis Set	IProg	
16.2.7.2	Treatment-Emergent Serious Adverse Events (TESAEs) – Safety Analysis Set	IProg	
16.2.7.3	Treatment-Emergent Adverse Events of Special Interest (AESIs) – Safety Analysis Set	IProg	

Listing Number	Listing Title	Validation Method	Shell Number (if Repeat)
16.2.7.4	Deaths – Safety Analysis Set	IProg	
16.2.7.5	Pre-Treatment Adverse Events – Screening Analysis Set	IProg	
16.2.8	Individual Laboratory Measurements and Other Safety		
16.2.8.1	Haematology – Safety Analysis Set	IProg	
16.2.8.2	Chemistry – Safety Analysis Set	IProg	16.2.8.1
16.2.8.3	Urinalysis – Safety Analysis Set	IProg	16.2.8.1
16.2.8.4	Clinically Significant Laboratory Values – Safety Analysis Set	IProg	
16.2.8.5	Urine Drug Screen – Safety Analysis Set	IProg	
16.2.8.6	Pregnancy Test – Safety Analysis Set	IProg	
16.2.8.7	Vital Signs Data – Safety Analysis Set	IProg	
16.2.8.8	Clinically Important Vital Signs Values – Safety Analysis Set	IProg	16.2.8.4
16.2.8.9	ECG Data – Safety Analysis Set	IProg	
16.2.8.10	Clinically Important ECG Values – Safety Analysis Set	IProg	
16.2.9	Other Study Instruments		
16.2.9.1	Mini International Neuropsychiatric Interview (MINI, Version 7.0.2) – Safety Analysis Set	IProg	
16.2.9.2	Columbia Suicidal Severity Rating Scale (C-SSRS) – Safety Analysis Set	IProg	
16.2.9.3	Brief Psychiatric Rating Scale – Positive Symptom subscale (BPRS+) – Safety Analysis Set	IProg	

1. BACKGROUND

This document details changes and / or additions to the planned statistical analyses for Compass Pathfinder Limited protocol COMP 201 study previously described in version 1.0 of the Statistical Analysis Plan (SAP) dated 05-March-2024.

These amendments were made post database lock but since the study was open label there was no unblinding step.

Rationale for Addendum:

1. To include instructions on how to derive the CAPS-5 cluster severity scores to be able to summarise, graphically display, and list these scores.
2. To include a summary of concomitant medications relative to COMP360 dose (i.e. medications that were taken pre-dose, post-dose, and overall).
3. To include individual participant plots of the CAPS-5 total scores.
4. To include details of scatter plots with Spearman's rank correlation coefficients to be produced for each dimension of the 5D-ASC on the x-axis and change from baseline in CAPS-5 total score on the y-axis.
5. To clarify in Section 11.2 that only individual item scores for the Resilience Adult Scale (RAS) are to be listed.
6. To remove Table 14.1.3.10 'Life Event Checklist for DSM-5 (LEC-5) – Safety Analysis Set' in Section 16 as this summary is redundant as this information is incorporated into Table 14.1.3.8 'Other Baseline Characteristics – Safety Analysis Set'.
7. To include a summary table and listing to report results for the Modified Discontinuation Emergent Signs and Symptoms Scale (mDESS).

2. CHANGES TO EXISTING SAP

2.1 Change 1

2.1.1 Original text: Section 9.6 Prior and Concomitant Medications

Prior and concomitant medications will be summarised (*Table 14.1.3.2* and *Table 14.1.3.3*) and listed (*Listing 16.2.4.6* and *Listing 16.2.4.7*).

2.1.2 Revised Text

Prior medications will be summarised (*Table 14.1.3.2*) and listed (*Listing 16.2.4.6*).

QMD Ref: Worldwide-TMP-ST-056-1.0_Effective: 12Aug2022	Governing QMD: Worldwide-SOP-ST-026
Confidentiality Statement	

This document is the property of Worldwide Clinical Trials Inc. and may not be duplicated, copied, altered or removed from company without prior approval from Worldwide Quality Assurance or in compliance with Worldwide Standard Operating Procedures.

Worldwide Clinical Trials Controlled Quality Management Document			
 WORLDWIDE CLINICAL TRIALS	Sponsor:	Compass Pathfinder Limited	Protocol Number:
POST DATABASE LOCK STATISTICAL ANALYSIS PLAN ADDENDUM			

Concomitant medications will be summarised by medications that were taken pre-dose, post-dose (including the medications that were started pre-dose but increased in dose post-dose), and overall (*Table 14.1.3.3*).

Concomitant medications will be listed (and *Listing 16.2.4.7*), and a separate listing will be produced containing only the medications that were started post-dose, including the medications that were started pre-dose but increased in dose post-dose (and *Listing 16.2.4.12*).

2.2 Change 2

2.2.1 Original text: Section 11.2 Additional Efficacy Endpoint(s)

The RAS total score will be listed (*Listing 16.2.6.6*).

2.2.2 Revised Text

The RAS item scores will be listed (*Listing 16.2.6.6*).

2.3 Change 3

2.3.1 Original text: Section 16 TABLES, FIGURES AND LISTINGS

14.1.3.10	Life Event Checklist for DSM-5 (LEC-5) – Safety Analysis Set	IProg
-----------	--	-------

2.3.2 Revised Text

14.1.3.10	Life Event Checklist for DSM-5 (LEC-5) – Safety Analysis Set	IProg
-----------	--	-------

3. ADDITIONS TO EXISTING SAP

3.1 Addition 1

3.1.1 New text: Section 8.4.1.4 CAPS-5 Clusters

The CAPS-5 cluster severity scores are calculated by summing the individual item severity scores for the symptoms contained in each DSM-5 diagnostic criterion for PTSD as shown in Table 10. The sum of the symptoms in cluster B correspond to the intrusion symptoms criterion, the sum of cluster C symptoms correspond to the avoidance symptoms criterion, the sum of cluster D corresponds to the negative alterations in cognitions and mood criterion, and the sum of cluster E corresponds to the arousal and reactivity criterion.

QMD Ref: Worldwide-TMP-ST-056-1.0_Effective: 12Aug2022	Governing QMD: Worldwide-SOP-ST-026
Confidentiality Statement	

This document is the property of Worldwide Clinical Trials Inc. and may not be duplicated, copied, altered or removed from company without prior approval from Worldwide Quality Assurance or in compliance with Worldwide Standard Operating Procedures.

Worldwide Clinical Trials Controlled Quality Management Document			
 WORLDWIDE CLINICAL TRIALS	Sponsor:	Compass Pathfinder Limited	Protocol Number:
POST DATABASE LOCK STATISTICAL ANALYSIS PLAN ADDENDUM			

3.2 Addition 2

3.2.1 New text: Section 10.7 mDESS

The total number of items on the mDESS, endorsed by the participant as being: (i) ‘new symptom(s)’; (ii) ‘old symptom(s) but worse’; and (iii) ‘new symptom(s)’ and ‘old symptom(s) but worse’, will be summarised by visit (*Table 14.3.6.7*).

mDESS data will be listed (*Listing 16.2.9.7*).

3.3 Addition 3

3.3.1 New text: Section 11.1.1 Main Analysis

Individual participant plots will be produced for the observed and change from baseline values for the CAPS-5 total score by timepoint (*Figure 14.2.2.7*).

3.4 Addition 4

3.4.1 New text: Section 11.2 Additional Efficacy Endpoint(s)

Scatterplots will also be created, for each dimension of the 5D-ASC on the x-axis and the change from baseline in CAPS-5 total score on the y-axis. A regression line overlaying the scatterplot will be included along with Spearman’s rank correlation coefficient, added in the plot area (*Figures 14.2.3.3 and 14.2.3.4*) for CAPS-5 change from baseline at Week 4 and Week 12 respectively.

Sample SAS code to estimate the Spearman correlation coefficient is provided below:

```
ods output FisherSpearmanCorr = corr;
proc corr data =  fisher spearman;
  var <caps-cfb> <5d-asc>;
run;
```

The CAPS-5 cluster scores and their changes from baseline will be summarised, graphically displayed, and listed (*Table 14.2.3.4, Figure 14.2.3.2, Listing 16.2.6.1*).

Table Number	Table Title	Validation Method

QMD Ref: Worldwide-TMP-ST-056-1.0_Effective: 12Aug2022	Governing QMD: Worldwide-SOP-ST-026
Confidentiality Statement	

This document is the property of Worldwide Clinical Trials Inc. and may not be duplicated, copied, altered or removed from company without prior approval from Worldwide Quality Assurance or in compliance with Worldwide Standard Operating Procedures.

Worldwide Clinical Trials Controlled Quality Management Document			
 WORLDWIDE CLINICAL TRIALS	Sponsor:	Compass Pathfinder Limited	
POST DATABASE LOCK STATISTICAL ANALYSIS PLAN ADDENDUM			

14.2.3.4	Additional Endpoint – Summary of Clinician-Administered PTSD Scale for DSM-5 (CAPS-5) Cluster Scores and Change from Baseline – Full Analysis Set	IProg
14.3.6.7	Summary of mDESS Symptom Scores by Visit – Safety Analysis Set	IProg

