2. Diagnosis of complex PTSD according to the International Trauma Questionnaire (ITQ)
3. McLean Screening Instrument for Borderline Personality Disorder (MSI-BPD) score ≥ 7 at screening. NOTE: participants positive for BPD will be subject to clinical confirmation of diagnosis by the study clinician and Medical Monitor
4. Significant suicide risk as defined by (1) suicidal ideation as endorsed on items 4 or 5 on the C-SSRS within the past year, during screening or at baseline, or; (2) suicidal behaviours within the past year, or; (3) history of serious suicide attempt that

required a rescuing medical intervention, or; (4) clinical assessment of significant suicidal risk during participant interview

5. Current (within the last year) alcohol or substance use disorder as informed by DSM-5 assessed via the MINI 7.0.2 at screening
6. Other personal circumstances and behaviour judged to be incompatible with establishment of rapport or safe exposure to psilocybin
7. Exposure to psilocybin, or any other psychedelics, such as ayahuasca, mescaline, lysergic acid diethylamide (LSD), or peyote in the past year
8. Primary diagnosis of major depressive disorder within 6 months of study entry
9. Exposure to a traumatic experience in the past 3 months
10. Significant childhood physical or sexual abuse based on clinician judgment with the use of CTQ
11. Enrolment in a psychological therapy programme that will not remain stable for the duration of the study. Psychological therapies cannot be initiated within 21 days of baseline

General Medical Exclusion Criteria:

12. Women who are pregnant, nursing or planning a pregnancy. Male and female participants who engage in sexual intercourse which could result in pregnancy, must agree to use a highly effective contraceptive method (as listed in Section 8.5.2) throughout their participation in the study. Women of childbearing potential must have a negative urine pregnancy test at screening and baseline
13. Cardiovascular conditions: recent stroke (< 1 year from signing of ICF, recent myocardial infarction (<1 year from signing of ICF), hypertension (blood pressure >140/90 mmHg) or clinically significant arrhythmia within 1 year of signing the ICF
14. Uncontrolled diabetes for whom hypoglycaemia during a prolonged fasting period could be a concern
15. Seizure disorder

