6 ANALYSIS SETS

Table 3: Analysis Sets

Analysis Set	Definition
Screening Analysis Set	All participants who signed the ICF
Safety Analysis Set	All participants who receive study drug
Full Analysis Set (FAS)	All participants in the Safety Analysis Set

ICF: Informed consent form

The Safety Analysis Set will be used for all safety-related evaluations and study population-related evaluations.

The Full Analysis Set (FAS) will be used for all efficacy-related evaluations.

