8.3.7 Modified Discontinuation Emergent Signs and Symptoms Scale (mDESS)

The mDESS is a 15-item, self-reported scale, listing typical symptoms that can arise from antidepressant withdrawal.⁸ If participants will be required to withdraw from prohibited medications, they will be asked to class each of the 15 symptoms as new, old but worse, old but improved, old but not changed, and not present. A total score ranging from 0 to 15 is calculated by summing the number of ‘new symptom(s)’ and the number of ‘old symptom(s) but worse’.

mDESS data will be obtained at each visit during the screening period (V1b onwards) and at Baseline in the subset of participants who are withdrawing from prohibited medication/s during the screening period.

8.3.8 *Missing Data*

8.3.8.1 *Missing/Partial Start/Stop Dates of AEs*

Missing and partial start and stop dates will be imputed for analysis purposes as detailed below.

Partial or missing stop date will be imputed as follows:

- If the stop date is completely missing and the event has resolved the stop date will be imputed as the date of the participant's last clinic visit in the study
- If only the stop date year is known, and it is equal to the year of the participant's last clinic visit in the study, the stop date will be imputed as the date of the participant's last clinic visit date, otherwise if the year differs it will be imputed as "31-Dec"
- If the stop date month and year are known, the stop date will be imputed as the last day of that month unless the stop date is in the same month as the participant's last clinic visit in which case the date of participant's last clinic visit in the study will be used

Missing start date will be imputed as follows:

- If the stop date occurs on or after the dose of COMP360 or the AE is ongoing, the start date will be imputed as the date of the dose of COMP360
- If the stop date occurs before the dose of COMP360, the start date of the AE will be imputed as the participant's Screening date or the stop date of the AE whichever the earlier

Partial start date (year present, but month and day missing) will be imputed as follows:

- If the stop date occurs on or after the dose of COMP360 or the AE is ongoing, and the year is the same as the year of dosing the start date will be imputed as the date of the dose of COMP360. If the year is different from the year of dosing "01-Jan" will be used

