3.5 New text: Section 16 TABLES, FIGURES AND LISTINGS

Figure Number	Figure Title	Validation Method
14.2.2.7	Secondary Endpoint – Individual Participant Plot of Clinician-Administered PTSD Scale for DSM-5 (CAPS-5) – Full Analysis Set	IProg
14.2.3.2	Additional Endpoint – Summary of Clinician-Administered PTSD Scale for DSM-5 (CAPS-5) Cluster Scores and Change from Baseline – Full Analysis Set	IProg
14.2.3.3	Additional Endpoint - Scatterplot of Change from Baseline in CAPS-5 at Week 4 vs 5D-ASC Dimensions – Full Analysis Set	Stat IProg
14.2.3.4	Additional Endpoint - Scatterplot of Change from Baseline in CAPS-5 at Week 12 vs 5D-ASC Dimensions – Full Analysis Set	Stat IProg

Listing Number	Listing Title	Validation Method
16.2.4.1 2	Post-COMP360 Administration Concomitant Medications – Safety Analysis Set	IProg
16.2.9.7	Modified Discontinuation Emergent Signs and Symptoms scale (mDESS) – Safety Analysis Set	IProg

QMD Ref: Worldwide-TMP-ST-056-1.0_Effective: 12Aug2022	Governing QMD: Worldwide-SOP-ST-026
Confidentiality Statement	

This document is the property of Worldwide Clinical Trials Inc. and may not be duplicated, copied, altered or removed from company without prior approval from Worldwide Quality Assurance or in compliance with Worldwide Standard Operating Procedures.

Worldwide Clinical Trials Controlled Quality Management Document					
 WORLDWIDE CLINICAL TRIALS	Sponsor:	Compass Pathfinder Limited			
Protocol Number: COMP 201					
POST DATABASE LOCK STATISTICAL ANALYSIS PLAN ADDENDUM					

Approval for implementation of
Statistical Analysis Plan Post Database Lock Addendum

REVIEW / APPROVAL SIGNATURES

Plan Author [REDACTED] Senior Principal Statistician, Biostatistics Signature: [REDACTED]	Plan Reviewer, Worldwide [REDACTED] Statistician, Biostatistics Signature: [REDACTED]
Plan Approver, Sponsor Statistician [REDACTED] Senior Director, Statistics and Data Management Signature: [REDACTED]	Plan Approver, Sponsor Statistician [REDACTED] Statistician Signature: [REDACTED]

QMD Ref: Worldwide-TMP-ST-056-1.0_Effective: 12Aug2022	Governing QMD: Worldwide-SOP-ST-026
Confidentiality Statement	

This document is the property of Worldwide Clinical Trials Inc. and may not be duplicated, copied, altered or removed from company without prior approval from Worldwide Quality Assurance or in compliance with Worldwide Standard Operating Procedures.

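### The mDESS withdrawal table and listing cover only participants who were later dosed, so anyone who began withdrawal, has mDESS data and was not dosed is missing from both

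*SAP*

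**What the plan says.** SAP Section 8.3.7 describes the mDESS as a 15-item self-report of withdrawal symptoms. The total, 0 to 15, counts the symptoms that are new or that were present before and have worsened. It is collected at screening-period visits from V1b and at Baseline, "in the subset of participants who are withdrawing from prohibited medication/s during the screening period". SAP Table 2 schedules none after dosing.

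Version 1.0 of the SAP defined the scale but planned no output for it. The post-lock addendum adds a Section 10.7 with two outputs:

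- Table 14.3.6.7, "Summary of mDESS Symptom Scores by Visit – Safety Analysis Set"
- Listing 16.2.9.7, "Modified Discontinuation Emergent Signs and Symptoms scale (mDESS) – Safety Analysis Set"

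SAP Section 6 defines the Safety Analysis Set as "All participants who receive study drug" and assigns it to safety evaluations in general. It defines the Screening Analysis Set as "All participants who signed the ICF".

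For adverse events in the same pre-dose period, SAP Section 16 uses the wider set. Table 14.3.1.14 is titled "MedDRA Summary of Pre-Treatment Adverse Events (Aes) by Primary System Organ Class, and Preferred Term – Screening Analysis Set", and Listing 16.2.7.5 uses that set too. SAP Section 7 also undertakes to list the data of every individual participant.

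**The concern.** The outputs are meant to show what happens to people while they come off prohibited medication. Entry to them is decided afterwards, by whether the person went on to receive COMP360, and that can depend on how the withdrawal went. Someone with marked symptoms who goes back on medication, withdraws consent or fails eligibility at baseline is dropped, possibly because of what the table measures.

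Withdrawal is required by the protocol for those taking these drugs, and Protocol Section 7.2.1 gives safe discontinuation as a reason for the weekly screening visits. A reader would naturally take Table 14.3.6.7 as the account of how withdrawal was tolerated. As planned, it describes only those who got through to dosing, and it does not show how many others there were.

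**Working it through.** The documents give no figure to reproduce. The check sets the definitions side by side; the arithmetic that follows is illustrative only.

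**1. Who has mDESS data.** Participants withdrawing from prohibited medication who reached V1b or later (SAP Section 8.3.7; SAP Table 2, footnote 13).

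**2. Who is in the outputs.** Only those subsequently dosed (addendum titles; SAP Section 6).

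**3. What lies between the two.** After the first mDESS a participant must still:

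- have come off prohibited medication successfully at least two weeks before baseline (Protocol Section 6.2, inclusion 6);
- have no disqualifying suicidality. The Protocol synopsis, exclusion 4, names "suicidal ideation as endorsed on items 4 or 5 on the C-SSRS within the past year, during screening or at baseline"; Section 6.3 says at screening rather than during it;
- meet the remaining criteria, with no deviations permitted (Section 6.5);
- pass the final eligibility review after baseline (Section 7.2.2).

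The first two are plausibly related to withdrawal symptoms. A participant who has mDESS data and fails any of the four is in neither output, and no other part of the SAP places mDESS on a wider set.

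**4. Comparison with other pre-dose outputs.**

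| Output | Set |
|---|---|
| Pre-treatment AEs, Table 14.3.1.14 and Listing 16.2.7.5 | Screening |
| Screen-failure reasons, Table 14.1.1.3 | Screening |
| Inclusion and exclusion criteria, Listings 16.2.4.4 and 16.2.4.5 | Screening |
| mDESS, Table 14.3.6.7 and Listing 16.2.9.7 | Safety |

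The mDESS outputs therefore describe different people from the AE summary of the same period, and the listing falls short of SAP Section 7.

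**5. Possible size (all inputs assumed).** Let d be the dosed and k the undosed participants who began withdrawal and have mDESS data, with mean scores a and b.

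- Mean over all = (d·a + k·b)/(d + k)
- Shortfall of the planned table = k(b − a)/(d + k)

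With a = 3:

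| d | k | b | Mean over all | Shortfall |
|---|---|---|---|---|
| 10 | 0 | any | 3.0 | 0 |
| 10 | 2 | 3 | (30 + 6)/12 = 3.0 | 0 |
| 10 | 2 | 6 | (30 + 12)/12 = 3.5 | 0.5 |
| 10 | 2 | 10 | (30 + 20)/12 = 4.17 | 1.17 |
| 5 | 5 | 6 | (15 + 30)/10 = 4.5 | 1.5 |
| 5 | 5 | 10 | (15 + 50)/10 = 6.5 | 3.5 |

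Over d = 5 to 15 and k = 0 to 5, the shortfall runs from 0 to 1.5 points if b = 6 and from 0 to 3.5 points if b = 10. It is zero if k = 0 or b = a, and changes sign if b < a. The table is by visit, so this would apply to each visit's mean separately.

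**The case against.** **Much of the harm is reported elsewhere.** This is largely right. Protocol Section 8.2.1 requires a positive answer on C-SSRS ideation items 4 or 5, or on any suicidal behaviour item, to be reported as an AE or SAE. AEs are recorded from consent, so such an event in an undosed participant should reach Table 14.3.1.14 and Listing 16.2.7.5. A failed discontinuation or an exclusion for suicide risk should appear in Table 14.1.1.3 and Listings 16.2.4.4 and 16.2.4.5. What these do not replace is the symptom-level record. AE enquiry is general and does not prompt for specific symptoms (Protocol Section 11.1), whereas the mDESS asks about 15 named ones.

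**The screening-period C-SSRS.** Table 14.3.6.4, "Summary of C-SSRS by Visit – Safety Analysis Set", also covers dosed participants only. A reader might infer that its pre-dose cells for items 4 and 5 can only be zero, or that suicidality in screening is reported only for dosed participants. The documents support neither. SAP Section 8.3.5 uses a lifetime version at Screening, and the exclusion reaches back only one year, so lifetime endorsements can occur in dosed participants. The synopsis and Section 6.3 differ on whether the exclusion clearly covers Visits 1a, 1b and onward. The AE route carries serious endorsements in undosed participants.

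**The direction is not certain.** Participants can go undosed for reasons unrelated to withdrawal, such as the CAPS-5 threshold, a urine drug screen, blood pressure or pregnancy, and need not have high mDESS scores. This stands: understatement is an expectation, not a finding.

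**mDESS is not an endpoint, and the set follows the general rule.** Both are true. The primary objective concerns COMP360, and describing the withdrawal state of those who were dosed has its own use. But the SAP already departs from the general rule for pre-treatment AEs, and a dosed/not dosed split keeps the description of the dosed group.

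**Conclusion.** The point holds for one table and one listing. By definition, both leave out every participant who began withdrawal, has mDESS data and was not dosed. If there are such participants, the summary probably understates withdrawal symptoms, because some of the reasons for not being dosed are plausibly linked to them. The assumed scenarios give a shortfall of 0 to 3.5 points on the 0–15 scale. They show only how the restriction could work, since the documents do not say how many tapered or how many of those went undosed.

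A reader might go further and infer that the trial understates the harm of withdrawal. The documents do not support that: no undosed taperer is shown to exist, and AEs and eligibility failures in undosed participants are reported on the Screening Analysis Set.

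One further limit applies. The supplied protocol does not mention the mDESS, while the SAP cites protocol V5.0. The eligibility steps above are those of the supplied text.

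**What to change.** Produce Table 14.3.6.7 and Listing 16.2.9.7 for all Screening Analysis Set participants who began withdrawal of a prohibited medication, split by dosed and not dosed. State the number who began withdrawal, the number with mDESS data, the number dosed and the reasons for not dosing. If every participant with mDESS data was dosed, these counts show that nothing is missing.

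Add a note that collection starts at V1b while tapering starts at V1a (Protocol Section 7.2.1). Anyone who stopped in between has no mDESS data, and a change of set cannot recover them. Optionally, list the screening-period C-SSRS for the same participants; the post-dose C-SSRS can stay on the Safety Analysis Set.

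The cost is a change of population and one added split in one table and one listing, plus a few counts. No new data are needed. The addendum was itself written after database lock in an open-label study, so the sponsor can count these participants now.
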